3.4 Additional Outcomes

Additional outcomes have been included due to a) interest from the study team and b) to reflect those intermediate outcomes in the Pregnancy Circles logic model which are not included as secondary outcomes (see Wiggins et al., 2020). Additional outcomes have been listed separately from secondary outcomes to avoid multiplicity issues due to an excessive number of secondary outcomes and are to serve predominantly for hypothesis generation.

- 1. Social support using Duke Social Support Scale (continuous: scores range from 8-40, higher scores favoured)
- Self-efficacy using Perlin Mastery Scale (continuous: scores range from 7-28 with higher scores favoured)
- 3. Prenatal stress using Revised Prenatal Distress Questionnaire (continuous: 12-item total score, scores range from 0-16; higher is favoured)
- 4. Health literacy using Health Literacy Questionnaire (continuous: score on only first domain of HLQ, range 1-20, higher score favoured)
- 5. Attendance at antenatal care (continuous: number of sessions, higher is favoured)
- 6. Additional measures of satisfaction with care (categorical: (FU1) Overall, how do you feel about the care you received from midwives? Options very happy, fairly happy, not very happy, very unhappy; (FU2) Overall, how do you feel about the care you received from midwives (before the birth of your baby)? options very happy, fairly happy, not very happy, very unhappy)
- 7. Caesarean delivery (categorical: planned, emergency, none)
- 8. Infant birth weight in grams (continuous)
- 9. Place of birth (categorical: actual place of delivery; options= hospital obstetric unit, hospital alongside midwifery unit, freestanding midwifery unit, home or other)

- 10. Breast feeding continuation and exclusivity (binary: did mother exclusively breastfeed to 3-month follow-up, yes favoured --> however will look at exclusive, breast milk, artificial exclusive, mixed, other in descriptive analysis)
- 11. Postnatal depression using Edinburgh Postnatal Depression Scale (binary: mothers scoring above 13 are "likely to be suffering from a depressive illness of varying severity", no favoured)
- 12. Postnatal symptoms using NPEU (National Perinatal Epidemiology Unit) checklist (based on the NPEU checklist items to produce a single score variable; continuous; lower scores favoured from 0 to 5). The items include psychological symptoms (e.g. "the blues", depression, anxiety); posttraumatic stress-type symptoms (e.g. flash-backs, difficulties concentrating, sleep problems not related to the baby); bodily changes (e.g. stress incontinence, backache; difficulties/pain during intercourse); birth-related symptoms (e.g. painful stitches, wound infection); breastfeeding problems and severe fatigue.
- 13. Immunisation (categorical: Has your new baby had their routine immunisations at 2 months and 3 months of age? Options yes 2 months; no 2 months; yes 3 months; no 3 months)
- 14. Continuity of antenatal care (categorical: how many midwives did you have during care; options=1-2, 3, 4+ or don't know with 1-2 being favoured) and satisfaction with continuity (categorical: Do you feel in general that the midwives you saw during your regular antenatal appointments got to know you and remembered you and your progress? Options yes definitely; yes, a little; no, not really; no, not at all; don't know can't remember; How satisfied are you with how much midwives got to know you and remember you and your progress? Options very satisfied; quite satisfied; not at all satisfied; don't know/can't remember; Do you feel that midwives have been sensitive to your cultural and/or language needs? Options yes, definitely; yes, a little; no, not at all; don't know/can't remember)
- 15. Choice in care (categorical: Were you offered any of the following choices about where to have your baby? Options a choice of different hospitals; in a midwife-led unit or a birth centre; in a consultant-led unit; at home; I was not offered any choices; I was not offered any choices due to medical reasons; don't know)
- 16. Involvement in care (categorical: Thinking about your regular antenatal care, do you think you were involved enough in decisions about your care? Options yes, always; yes sometimes; no and I wanted to be; no and I did not want to be; don't know)
- 17. Preparedness for labour and birth (categorical: How prepared did you feel for labour and birth? options: very well, quite well, not very well and not at all well and How well did you manage during labour? options very well, quite well, not very well and not at all well)
- 18. Confidence in caring for baby after birth (categorical: How confident did you feel about caring for your baby in the first week after the birth?: options very confident, fairly confident, not very confident, not at all confident, don't know/can't remember and Have you received enough help and advice from a midwife and/or health visitor about your baby's health, care and progress? Options yes, definitely; yes to some extent; no, and I wanted help/advice; no, but I did not need any; don't know)

4. Study methods

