1.6 Remit of SAP

REACH is a programme grant. This SAP covers outcomes from work package 3 (Pregnancy Circles Trial). This plan is intended not to change or contradict the general aims of the protocol, but rather expand on them. In the event of a discrepancy the analyses described here will supersede those in earlier documents.

2. Background and trial design

Study objectives	This trial study objectives are as follows:
	a. To assess whether Pregnancy Circles (group-based antenatal
	care) improves the health of babies compared with the standard
	individual model of antenatal care.
	b. To assess whether attending Pregnancy
	Circles improves maternal outcomes such as empowerment
	and post-natal depression, as well as increasing women's
	satisfaction with antenatal care.
	c. To assess cost-effectiveness, intervention mechanisms, and
	acceptability of group-based antenatal care to women and
	staff and issues relevant to future sustainability and wider
	implementation in the NHS.
Study design	Individually randomised, parallel group, randomised controlled
	superiority trial with integrated process and economic evaluations
Setting	Multi-centre study across 14 NHS Trusts, namely Barts Health NHS
	Trust, Whittington Hospital NHS Trust, Lewisham & Greenwich NHS
	Trust, West Hertfordshire NHS Trust, East Suffolk and North Essex NHS
	Foundation Trust, Princess Alexandra Hospital NHS Trust,
	Worcestershire Acute Hospitals NHS Trust, Mid and South Essex NHS
	Foundation Trust, Ashford and St Peter's Hospitals NHS Foundation,
	East Sussex Healthcare NHS Trust, Lancashire Teaching Hospitals NHS
	Foundation Trust, Surrey and Sussex Healthcare NHS Trust, Epsom &
	St. Helier University Hospitals NHS Trust and Royal Free London NHS
	Foundation Trust
Participants	Women who are currently pregnant and registered for antenatal care
	with the included NHS Trust maternity services, whose estimated due
	dates fit with the proposed group start dates, and who live within the
	usual working areas of these services
Interventions	Intervention
interventions	Pregnancy circles consisting of 8-12 pregnant women, facilitated by
	two midwives (and supplemented with interpreters and/or other
	support staff as appropriate). There will be a total of eight antenatal
	group sessions each of which will last for approximately two hours.
	The first part of each session will involve "self-care activities" (ex.
	Women will be encouraged to take an active part in their antenatal

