5.9 Analysis of primary, secondary and additional outcomes

The following table shows the variable type of outcomes in this study:

		•
	Outcomes:	
Binary	Continuous	Categorical
-healthy baby composite	-attendance at antenatal care	-continuity of care
-spontaneous vaginal delivery	-women's empowerment	-Caesarean delivery
-breast feeding initiation	-social support	-place of birth
-breastfeeding continuation	-self efficacy	- additional measures of
-postnatal depression	-prenatal stress	satisfaction
-live baby	-health literacy	- choice and involvement in
-born at term	-mental wellbeing	care
-appropriate weight for	-postnatal symptoms	- preparedness for labour
gestational age	-satisfaction with care	- confidence in caring for baby
-not admitted to a neonatal	-Infant birth weight in grams	- immunisation
care unit		

Main analysis model (binary outcome)

The primary outcome data for the 'Healthy Baby' composite will be extracted via a postpartum maternity records audit and be analysed using a nested multilevel logistic mixed effects model with two random intercepts estimating a cluster and site-specific effects in both arms (1). Although site is a stratification factor, it has been included as a random effect due to the high number of sites included. In the intervention arm, within Pregnancy Circle cluster correlation will be accounted for and in the control arm each participant will be modelled as a cluster of size 1. The other stratification factor used in this trial is the ability to speak English and will be included as a fixed effect covariate. The resulting model will produce an odds ratio for the odds of giving birth to a 'healthy baby' in the intervention versus the control arm. The outcome will be assessed at the participant's level (mother) following this rule: if a mother has multiple births for the same delivery (e.g. twins), the 'Healthy Baby' composite will be equal to 'yes' only if all babies are healthy. Otherwise, Healthy baby will be equal to 'no'.

Specifically, let y be the binary outcome, i is the individual participant indicator (mother), j is the pregnancy circle indicator, t is the intervention indicator (0 = control, 1 = intervention), θ is the intervention effect, θ_0 is an intercept term, I is the site indicator, and θ_{ki} represents further covariates (ability to speak English in this instance). Then,

$$Logit[Pr(y_{iil}=1)] = \beta_0 + \theta t_i + \beta_{ki} + v_l + u_i$$

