where $u_j \sim N(0, \sigma^2_u)$ is a random-effects term representing between-cluster (pregnancy circle) variation in the clustered intervention arm and $v_l \sim N(0, \sigma^2_w)$ is the random effect representing between-site variation.

Accounting for non-collapsibility

Odds ratios present the characteristic of non-collapsibility when adjusted on covariates. To deal with that phenomenon, the g-computation estimator will be used for covariate adjustment following the 6 steps described below as described in the FDA's guidance for covariate adjustment [13]:

- (1) Fit a logistic model with maximum likelihood that regresses the outcome on allocation assignments and prespecified baseline covariates. The model will include an intercept term.
- (2) For each subject, regardless of allocation assignment, compute the model-based prediction of the probability of response under pregnancy circle group using the subject's specific baseline covariates.
- (3) Estimate the average response under pregnancy circle group by averaging (across all subjects in the trial) the probabilities estimated in Step 2.
- (4) For each subject, regardless of allocation assignment, compute the model-based prediction of the probability of response under usual care using the subject's specific baseline covariates.
- (5) Estimate the average response under usual care by averaging (across all subjects in the trial) the probabilities estimated in Step 4.

The estimates of average responses rates in the two allocation groups from Steps 3 and 5 will be used to estimate an unconditional intervention effect. Risk differences, and odds ratios will both be presented for primary and secondary outcomes. Confidence intervals will then be estimated using bootstrap.

Any of the secondary or additional outcomes which provide binary responses (spontaneous vaginal delivery, infant low birthweight, etc.) will be analysed using the same nested multilevel logistic mixed effects model.

Analysis of continuous outcomes

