Primary outcome is in bold and underlined and secondary outcomes are in bold and italic

^{*} PC for Pregnancy Circle group

^{**} ICC for clustering in intervention group (cluster is PC group)

^{***} Confidence interval is established using Swiger's method

Table 3: Results of secondary and additional continuous outcomes at 35 weeks and 3 months post-partum

	Number in	cluded in	Summary	measure	Treatment	effect		
	analy	/sis	-					
Outcome	Usual care	PC	Usual care	PC	Mean	(95% CI)	p-value	ICC**
	n (%)	n (%)	Mean (SD)	Mean (SD)	difference			[95 % CI]***
Pregnancy-								
related								
Empowerment								
Scale (PRES)								
Range 16-64								
Week 35								
Friends and								
family test								
Range 1-5								
Week 35								
Month 3 pp								
Emotional								
Wellbeing								
(SWEMWBS)Ra								
nge 7-35								
Week 35								
The Duke-UNC								
Functional								
Social Support								
Questionnaire								
Range 8-40								
Month 3 pp								
Pearlin								
Mastery Scale								
Range 7-28								
Month 3 pp								
Revised								
prenatal								
distress scale								
Range 0-16								
Week 35								
Infant birth								
weight (g)								
Month 3 pp								
Health literacy								
Range 1-20								
Week 35								

Post natal				
symptoms				
(NPEU)				
Range 0-5				
Month 3 pp				
Number of				
antenatal care				
sessions				
attended				

Secondary outcomes are in bold and italic

Table 4: Analysis of categorical Additional Outcomes

	Number include	ed in analysis	Summary	measure	
Outcome	Usual care n (%)	PC n (%)	Usual care %	PC %	P value for between group difference
How do you feel about the care you received					
from midwives? (week 35)					
very happy					
fairly happy					
not very happy					
very unhappy					
Missing					
How do you feel about the care you received					
from midwives (before the birth of your					
baby)? (3 months pp)					
very happy					
fairly happy					
not very happy					
very unhappy					
Missing					
Caesarean delivery					
Planned					
Emergency					
None					
Missing					
Place of birth					
Hospital obstetric unit					
Hospital alongside midwifery unit					
Freestanding midwifery unit					
Home					
Other					
Missing					

^{*}PC is for Pregnancy Circle group

^{**} ICC for clustering in intervention group (cluster is PC group)

^{***} Confidence interval is established using Swiger's method

Has your new baby had their routine		
immunisations?		
Yes 2 months		
No 2 months		
Yes 3 months		

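### Postnatal depression, named in objective (b), is analysed only as EPDS above or below a cut; adding the EPDS total score would recover much of the precision at almost no cost

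*SAP*

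**What the plan says.** Section 2 (Study objectives) sets objective (b): to assess whether attending "Circles improves maternal outcomes such as empowerment" "and post-natal depression, as well as increasing women's" satisfaction with antenatal care. Depression is thus one of three outcomes named there.

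Empowerment and satisfaction are secondary outcomes 2 and 3 in section 3.3. Depression is additional outcome 11 in section 3.4: "Postnatal depression using Edinburgh Postnatal Depression Scale (binary: mothers scoring above 13 are 'likely to be suffering from a depressive illness of varying severity', no" being the favoured answer. Section 3.4 says that additional outcomes are listed apart to limit multiplicity, and that they "are to serve predominantly for hypothesis generation".

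Section 5.9 lists "postnatal depression" in the binary column only. Secondary and additional binary outcomes "will be analysed using the same nested multilevel logistic mixed effects model" as the primary outcome. Table 2 in section 8.4 has a row for depression at month 3, with columns for odds ratio, risk difference, p-value and ICC. No EPDS score appears among the continuous outcomes of section 5.9 or in Table 3.

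On mental wellbeing, section 3.1 shows SWEMWBS collected at baseline, 35 weeks and 3 months. Section 3.3, item 5, makes it a secondary outcome without naming a time point. The relevant dummy table is headed "Table 3: Results of secondary and additional continuous outcomes at 35 weeks and 3 months post-partum", but its SWEMWBS row lists Week 35 only.

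**The concern.** EPDS is the only multi-item scale in sections 3.3 and 3.4 that is reduced to a yes/no result. The empowerment scale, SWEMWBS, Duke, Pearlin, prenatal distress, health literacy and NPEU symptom measures are all analysed as scores. The SAP does not say why EPDS differs.

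A cut treats all women below it alike and all women above it alike. It therefore discards most of the variation in the questionnaire when few women lie above it. At stake is precision on an outcome that the objective names: a modest shift in depressive symptoms could be missed by the binary comparison when the same returned questionnaires would show it as a mean difference.

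The SWEMWBS gap is smaller and separate. A reader cannot tell whether the secondary endpoint is the 35-week score, the 3-month score or both.

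**Working it through.** **Own figure.** The SAP states no prevalence, standard deviation, effect size or power for EPDS, so there is no figure to reproduce on this point. What follows rests on stated assumptions.

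**Step 1: information kept by a cut.** For a normal score with a proportion p above the cut at z, and a small shift between arms, the efficiency of the binary comparison relative to the mean difference is

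RE = φ(z)² / [p(1 − p)].

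The standard error ratio is 1/√RE and the sample size ratio is 1/RE.

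| p above cut (assumed) | z | φ(z) | RE | SE ratio | Sample size ratio |
|---|---|---|---|---|---|
| 10% | 1.282 | 0.1755 | 0.0308/0.0900 = 0.342 | 1.71 | 2.92 |
| 13% | 1.126 | 0.2115 | 0.0447/0.1131 = 0.396 | 1.59 | 2.53 |
| 15% | 1.036 | 0.2332 | 0.0544/0.1275 = 0.426 | 1.53 | 2.35 |
| 20% | 0.842 | 0.2800 | 0.0784/0.1600 = 0.490 | 1.43 | 2.04 |

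**Step 2: does clustering change this?** Section 4.1.1 gives an ICC of 0.05 for the primary outcome, in the intervention arm only, with mean circle size 8 and Poisson variation. The design effect in that arm is 1 + (8 − 1 + 1) × 0.05 = 1.40. Suppose the same ICC held for the EPDS score. To first order, the ICC after the cut would be 0.05 × RE, which is 0.017 at 10% and 0.0245 at 20%. The design effects would be 1.137 and 1.196. Averaging over the two arms, the information kept becomes 0.342 × (2.40/2.137) = 0.38 and 0.490 × (2.40/2.196) = 0.54. Clustering therefore softens the loss slightly and does not remove it.

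**Step 3: what it could mean for power (illustration only).** Take 2190 − 298 = 1892 women, the set left after the pandemic exclusion in section 4.1.2. That exclusion is stated for the primary outcome, so using it here is an assumption. Assume also 50-80% response at 3 months (473 to 756 per arm), a shift of 0.2 SD, and a design effect of 1.40 in the intervention arm for both forms.

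- Score, 473 per arm: standard error = √(1/473 + 1.40/473) = 0.0712; 0.2/0.0712 − 1.96 = 0.85; power 80%.
- Score, 756 per arm: standard error = √(1/756 + 1.40/756) = 0.0563; 0.2/0.0563 − 1.96 = 1.59; power 94%.
- Cut: power 33-49% if 10% of controls lie above it, 41-59% if 15%, and 47-66% if 20%.

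By Step 2, the design effect of 1.40 is somewhat harsh on the cut, so the true gap would be a little narrower.

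**Step 4: time points, set side by side.** For SWEMWBS, section 3.1 has follow-up at 35 weeks and 3 months, section 3.3 gives no time, and Table 3 has Week 35 only. For the Friends and family test, section 3.1 has both times and Table 3 has both rows. For Pearlin, section 3.1 has both follow-up times but Table 3 has Month 3 only. The table is therefore not aligned with section 3.1 in more than one place.

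**The case against.** Much of the case on the other side stands.

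- The objective names depression, a condition, and item 11 ties the cut to likely depressive illness. A threshold proportion is clinically readable and is a legitimate analysis.
- The placement among additional outcomes is deliberate, and section 3.4 gives a reason: to limit the number of secondary outcomes. Promoting EPDS would reverse that choice. It is a trade-off, and nothing in the SAP requires every outcome named in an objective to be secondary.
- The size rests on an assumed prevalence and a normal score, neither of which is in the SAP.
- Table 3 is a dummy table, and SWEMWBS is not named in objective (b).

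A reader might go further and infer that the plan hardly tests objective (b), or that its postnatal part rests on one comparison. The document does not support this. Empowerment, satisfaction and wellbeing are all secondary outcomes. Depression has a full modelled comparison. The continuous NPEU symptom score, which includes depression and anxiety items, has a Month 3 row in Table 3, as do the Friends and family test, Duke and Pearlin.

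A reader might also infer that no conclusion on depression could be drawn. The word in section 3.4 is predominantly, which is not a bar. Section 5.5 sets the same two-sided 5% level for tests generally, and section 5.7 makes no multiplicity adjustment. The rank affects emphasis, and it leaves depression outside the subgroup analyses of section 5.12, but it does not change the test.

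The objection does not give a reason to leave the EPDS total score unanalysed. Reporting the score takes nothing away from the threshold result.

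**Conclusion.** The point holds as an inexpensive improvement to the plan; the existing EPDS analysis is not an error. With 10-20% of women above the cut and a roughly normal score, the binary form keeps about 34-49% of the information (about 38-54% if the SAP's ICC of 0.05 also applied to the score). Both the prevalence and the normality are assumptions, and a skewed score would change the figures. The power figures are an illustration, since effect size and response are assumed too.

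The finding does not require EPDS to become a secondary outcome, and it gives no ground for taking depression out of objective (b). The SWEMWBS time point is a minor matter of alignment, but it concerns a secondary outcome and should be settled.

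**What to change.** 1. In section 3.4, item 11, add the EPDS total score at 3 months as a continuous measure and keep the proportion above 13 as the clinically interpretable binary result. EPDS may stay an additional outcome.
2. In section 5.9, list the EPDS score among the continuous outcomes, so that the existing partially nested model applies. Section 3.1 shows EPDS at 3 months only, so no baseline score is involved.
3. In section 8.4, add an EPDS row at Month 3 to Table 3 and keep the depression row in Table 2.
4. In section 3.3, item 5, name the SWEMWBS time point or points, and add the Month 3 row to Table 3. Check the Pearlin row against section 3.1 at the same time.

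The cost is a few lines of SAP text and one additional model, with no new data. The downside is one more unadjusted comparison among the additional outcomes. The change should be dated before the analysts see unblinded data; if that point has passed, the EPDS score analysis should be labelled post hoc.

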3.1 Timing of outcome measures

Data on the various outcome measures used in this study will be collected either at baseline (recruitment; during the first antenatal booking appointment/first dating-scan appointment), first follow-up (35-weeks gestation), birth (routine maternity data) or second follow-up (3-months postnatal) or a combination of these time points. The table below shows the outcomes, the validated scales/measures which are being used where appropriate, and the specific time points when outcome data will be collected.

Outcome measure and data collection timing

Outcome	Validated measure (where applicable)	Baseline	First follow up - 35 weeks gestation	Birth – routine maternity data	Second follow up - 3 months postnatal
Live baby				√	
Born at term				✓	
Appropriate weight for gestational age	GROW centile >9.99 & <90.01			✓	
Not admitted to a Neonatal Care Unit				✓	
Spontaneous vaginal delivery (SVD)				√	~
Women's empowerment	Pregnancy-related Empowerment Scale (PRES)		√		
Women's satisfaction with maternity care	Friends and family test		✓		√
Attendance at antenatal care			√	√	
Social support	The Duke-UNC Functional Social Support Questionnaire	✓			✓
Self-efficacy	Pearlin Mastery Scale	√	✓		√

Prenatal stress	Revised prenatal distress scale	√	√		
Caesarean delivery				√	√
Infant birth weight (g)				1	
Place of birth				√	
Breast feeding initiation					✓
Breast feeding continuation and exclusivity					√
Postnatal depression	Edinburgh Postnatal Depression Scale (EPDS)				√
Health Literacy	Health Literacy Questionnaire (HLQ) (1 domain)		√		
Postnatal symptoms	(NPEU checklist)				✓
Emotional wellbeing	Short Warwick- Edinburgh Mental Wellbeing Scale (SWEMWBS)	√	✓		✓
Health related quality of life	EQ5D-5L	√	√		✓
Continuity with care			√		
Choice in care			√		√
Involvement in care					√
Preparedness for labour and birth			√		√
Confidence in caring for baby after birth					√
Immunisation					√

Additional			,
measures of		,	√
satisfaction with		V	
care			

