Secondary and additional outcomes providing continuous responses, such as a total score on any of the scales being used, will be analysed by assessing difference of means between intervention and control groups. This will be analysed using a partially nested mixed-effects model with heteroskedastic error terms with the Satterthwaite approximation for degrees of freedom to avoid upward bias of the type-I error rate (2). The English level will again be included as covariate in these models. The resulting model will estimate a difference of means between the intervention and control arms of the study. Specifically, let y be the continuous outcome, i is the mother participant indicator, j is the pregnancy indicator, t is the intervention indicator (0 = usual care, 1 = pregnancy circle), θ is the intervention effect, θ_0 is an intercept term, and θ_k represents fixed effects for English level. Then,

$$y_{ij} = \beta_0 + \theta t_{ij} + \beta_k + u_i t_{ij} + r_{ii} (1 - t_{ij}) + \epsilon_{ij} t_{ij} + v_1$$

where $u_j \sim N(0, \sigma^2_u)$ is a random-effects term representing between-cluster (pregnancy circle) variation in the clustered intervention arm, $r_{ij} \sim N(0, \sigma^2_r)$ represents individual-level variation in the

non-clustered control arm, $\epsilon_{ij} \sim N(0, \sigma^2_{\epsilon})$ represents individual-level variation in the clustered intervention arm and $v_i \sim N(0, \sigma^2_w)$ is the random effect representing between-site variation.

Analysis of categorical outcomes

For categorical outcomes, proportions by intervention group and test of between group difference without covariate adjustment will be presented.

Strategy for analysis of primary outcome if model fails to converge

In case the analysis of the primary outcome described above fails to converge, the following sequential strategy will be employed (starting at 1).

	Change from previous strategy
1	Try an alternative estimation algorithm, such as the
	QR decomposition in meqrlogit, rather than Stata's
	default melogit function.
2	Change the number of integration (quadrature)
	points for all levels using intpoints() command
3	Try an alternative integration method other than
	mean-variance adaptive Gauss-Hermite
	quadrature like Laplace for example.
4	Remove covariate English speaking level from the
	model.
5	Analysis using model, not assounting for clustering
5	Analyse using model, not accounting for clustering
	within intervention groups.

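### Immunisation at 2 and at 3 months is set up as one four-category variable, but the categories answer two questions and overlap, so one test across them is wrongly calibrated (conservative)

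*SAP*

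**What the plan says.** SAP section 3.4, item 13, puts one question and types the outcome as categorical: "Immunisation (categorical: Has your new baby had their routine immunisations at 2 months and 3 months of age". It gives the answers as "Options yes 2 months; no 2 months; yes 3 months; no 3 months". The outcome table in section 5.9 again places "immunisation" in the categorical column, not the binary one. For that column the plan is: "For categorical outcomes, proportions by intervention group and test of between group difference without covariate adjustment will be presented". In section 8.4, Table 4 has a single immunisation heading with the four answers as rows, one missing row for the block, and a column headed "P value for between group difference".

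The schedule in section 3.1 ticks immunisation once, at the "second follow-up (3-months postnatal" time point. The SAP gives no option for a baby not yet due, no completion window, and no rule for a mother who answers for both ages. The fallback in section 5.9 for awkward categorical outcomes is general and does not separate the two ages.

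**The concern.** The four rows are not the levels of one variable. Every baby has a status at 2 months and a status at 3 months, so a mother who answers fully puts her baby in two rows. Three things follow if the plan is carried out as laid out.

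- The percentages have no clear denominator: babies, or answers.
- One shared missing row cannot show which age is missing.
- A test across the four rows counts each such baby twice and is compared with the wrong reference distribution.

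A separate, lesser matter is timing. The 3-month answer is collected at the nominal 3-month follow-up, so some negative answers at that age may come from babies whose immunisation is not yet due. This concerns what the 3-month answer measures. It is not what upsets the p-value.

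What is at stake is the readability of one exploratory result and the calibration of its p-value.

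**Working it through.** The SAP states no figure for this outcome, so there is none to reproduce. The check has three parts.

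**1. Size of a single Pearson test over the four rows**

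Inputs: two-sided 5% level (section 5.5); a 2 × 4 table, arm by the four answers (section 3.4, Table 4). Assumptions: every mother answers both parts, and clustering is ignored.

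- Let arm *a* have n_a mothers, N in total. In the stacked table the arm total is 2n_a and the grand total is 2N. For an answer with total C, the expected count is 2n_a × C / 2N = n_a × C / N. This is the same expected count as in the separate 2 × 2 table for that age.
- Hence X²(four rows) = X²(2 months) + X²(3 months), each with 1 df under no effect.
- The standard reference is (2 − 1)(4 − 1) = 3 df, critical value 7.815.
- If the two answers are independent, the sum has 2 df: P = exp(−7.815 / 2) = 0.020.
- If the two answers are identical, the sum is twice a 1-df variable: P(χ²₁ > 7.815 / 2 = 3.907) = 0.048.

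**2. Simulation between these limits**

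Assumed inputs, none of them in the SAP: 400 or 700 responders per arm; 2-month uptake 90% or 95%; 3-month uptake 95% among babies who are due and had the 2-month doses; 50%, 80% or 100% of babies due at completion, equal in both arms; 4,000 runs per scenario; no clustering.

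| Test | Rejection rate under no effect, nominal 5% |
|---|---|
| One test over four rows | 2.2% to 4.0% |
| Separate 2-month test | 4.2% to 5.7% |
| Separate 3-month test | 4.4% to 5.6% |

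The separate tests keep their level within simulation error, including when half the babies are not yet due. An equal share of not-yet-due babies therefore does not raise the error rate.

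**3. Not-yet-due babies in the negative 3-month answer**

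Assume 95% uptake at each age, so that 0.95 × 0.95 = 0.9025 of babies who are due are immunised at 3 months. Let d be the share due at completion. Negative 3-month answers are then 1 − 0.9025d of all answers, and the not-yet-due part of them is (1 − d) / (1 − 0.9025d).

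| d (assumed) | Negative at 3 months | Of which not yet due |
|---|---|---|
| 100% | 9.8% | 0% |
| 90% | 18.8% | 53% |
| 80% | 27.8% | 72% |
| 50% | 54.9% | 91% |

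The range runs from nothing to nearly all. Without completion dates the SAP does not let one place the trial within it.

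**The case against.** The strongest reply is that the single test is inferred. Section 5.9 names no test, and no sentence says that one p-value spans the four rows. Table 4 also puts two time points under one heading elsewhere (choice of birthplace, preparedness, managing labour), so a heading there may stand for more than one comparison. The answers are labelled by age, and a statistician could report each age separately. This stands in part: the four-row test is the natural reading, not an explicit instruction. Against it, the outcome is typed as one categorical variable, the block has one missing row, and the plan does separate time points where it means to (the midwife-care question in Table 4, feeding in Table 5). Even without any test, the overlapping rows leave the denominators unclear.

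A reader might infer more than the document supports, in three ways.

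- *That the test yields false positives.* It does not: on the harshest reading it rejects too seldom. Clustering is left out of these figures. Positive correlation within circles would push the rate up, so the net size of the planned test is not known.
- *That every negative answer is contaminated by babies not yet due.* Only the 3-month answer can be, and how far depends on completion dates that the SAP does not give and the protocol may govern. A mother may also leave the item blank, or reply after the due date.
- *That reply timing biases the comparison of arms.* If 80% were due in one arm and 75% in the other, with 700 per arm and the 95% uptake above, a 3-month test would reject in 43% of runs with no true effect. But nothing in the SAP indicates such an imbalance. Allocation is known to participants (section 4.3), which makes it conceivable and no more.

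**Conclusion.** The point holds as a definition error in an additional outcome. Item 13 and its Table 4 block treat answers to two questions as categories of one variable. A baby with both answers appears twice, and on the natural reading the test has a true size of about 2% to 5% at nominal 5%. That range assumes that both parts are answered and that clustering is ignored.

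The timing of the 3-month item is a caveat on interpretation. It does not by itself invalidate a p-value, and its size cannot be settled from the SAP.

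The consequence is small. Section 3.4 offers the additional outcomes mainly to generate hypotheses, and no primary or secondary conclusion depends on this one.

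**What to change.** Replace item 13 with two binary outcomes, immunised at 2 months (yes/no) and immunised at 3 months (yes/no). Give each its own denominator, missing count, estimate and p-value. Move both to the binary column in section 5.9 and from Table 4 to Table 2. Section 5.9 already sends additional outcomes with binary responses to the multilevel logistic model, so no new method is needed, and circle and site are then accounted for.

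For the 3-month outcome, if completion dates are held, tabulate the baby's age at completion by arm and state that negative answers may include babies not yet due. Section 5.1 mentions a confirmed delivery date, but the SAP does not show that a questionnaire date is held, so this step is conditional. Do not restrict the analysis to replies after a fixed grace period: that selects on behaviour after randomisation. Do not reclassify only the early negative answers while keeping early positive ones: that would bias uptake upward.

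The cost is a change of wording, two table rows, and one more p-value among the additional outcomes. If uptake is very high the model may struggle to converge; the fallback sequence for binary outcomes in section 5.9 can then be applied.
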